2.1.1.3.3 Study week in observation periods

For subjects entered OBS1 prior to the treatment period, study weeks (OBS1 Week x) in the observation period are defined based on the study days and study day of start of OBS1 (Day b) as indicated in Table 2-3:

Table 2-3 **OBS1 Study Week definition based on Study Day, first observation period (for subjects entering first observation period on Day b prior to the second treatment period)**

OBS1 Study Week (x)	Study Days
OBS1 Week 1	Day $b \sim b + 6$
...	...
OBS1 Week x	Day $[7 \times (x-1) + b] \sim [7 \times x + b - 1]$
...	...
OBS1 Week 36	Day $[245 + b] \sim [b + 251]$

For subjects entered OBS2 prior to the second half of the treatment period, study weeks (OBS2 Week x) in the second observation period are defined based on the study days and study day of start of OBS2 (Day d) as indicated in Table 2-4:

Table 2-4 **OBS2 Study Week definition based on Study Day, first observation period (for subjects entering second observation period on Day d prior to the second half of the treatment period)**

OBS2 Study Week (x)	Study Days
OBS2 Week 1	Day $d \sim d + 6$
...	...
OBS2 Week x	Day $[7 \times (x-1) + d] \sim [7 \times x + d - 1]$
...	...
OBS2 Week 52	Day $[364 + d] \sim [d + 370]$

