3.4 Second observation period

- Visit 301 (Week 0) to 399 (Week 52 also referred to as End of Observation Period 2, EOBS2).
- If the subject's UAS7 is ≤ 6 at Week 52, the subject will enter the second (investigational treatment-free) observation period Visit 301 (Week 0) and will be assessed remotely (i.e. outside the clinic) by a safety phone call from the site every 4 weeks, unless there is an in-clinic visit scheduled.
- Subjects will have in-clinic safety and efficacy assessments done at 12 or 16 week intervals.
- Subjects must remain on the same H1-AH background medication they were taking in the preceding studies.
- Subjects should use the same H1-AH rescue medication that was agreed with the investigator at Visit 1 of this study.
- Use of oral corticosteroid rescue medication is **not permitted** during this second observation period.

- Subjects will continue to complete the eDiary twice daily as per protocol, in order to monitor the activity of their disease. All subjects should complete their eDiary for the 7 days prior to Visit 214 (i.e. one assessment-week) to ensure the UAS7 thresholds are available.
- Subjects who present with moderate to severe active disease ($UAS7 \geq 16$) will be brought back to clinic to be treated as soon as possible to perform Visit 214 (Week 52) in the second half of the treatment period) and restart treatment with ligelizumab 120 mg PFS q4w.
- Subjects with a $UAS7 < 16$ by the end of this second observation period will perform Visit 399 (EOOBS2) of this extension study to exit the study.
- Subjects who wish to discontinue from this observation period will be expected to complete at least Visits 301, 302 and 303 (Week 0, 4 and 8), and perform Visit 399 (Week 52/EOOBS2) and exit the study.

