The first visit of the extension study, if it cannot occur on same day as the last visit (Visit 1999) of the preceding studies, as described in [Section 3.1](#) and [Section 8.1](#), should occur within as short time as possible from the last visit of the preceding studies. In this case, the Investigator must perform a thorough review of new medical histories and concomitant medication changes from the time of the last visit of the preceding studies until the first visit of this extension study.

Assessment schedule ([Table 8-1](#) and [Table 8-2](#)) lists all of the assessments and when they are performed. All data obtained from these assessments must be supported in the subject's source documentation.

Subjects should be seen for all visits/assessments as outlined in the assessment schedule ([Table 8-1](#) and [Table 8-2](#)) or as close to the designated day/time as possible. Missed or rescheduled visits should not lead to automatic discontinuation. Subjects who prematurely discontinue the study or withdraw their consent/oppose the use of their data/biological samples for any reason should be scheduled for a visit as soon as possible, at which time all of the assessments listed for the final visit (Visit 9999/EOS) will be performed. At this final visit, all dispensed investigational product should be reconciled, and the AE and concomitant medications recorded on the CRF.

As per [Section 4.6](#), during a Public Health emergency as declared by Local or Regional authorities, i.e., pandemic, epidemic or natural disaster that limits or prevents on-site study visits, alternative methods of providing continuing care may be implemented by the investigator as the situation dictates. If allowable by a local Health Authority and depending on operational capabilities, phone calls or virtual contacts (e.g., tele consult), can replace on-site study visits, for the duration of the disruption until it is safe for the participant to visit the site again.

[figure not shown]
Table 8-1 Assessment Schedule (Screening, First and Second half of the treatment period and Follow-up period)

Epoch	Screening		-----First half of the Treatment----->																								-----Second half of the Treatment----->			
	Visit Numbers ¹	1 ²	2 ³	201	202	203	204	205	206	207	208	209	210	211	212	213	214 ^{4,5}	401	402	403	404	405	406	407	408	409	410	411	412	9998

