2.1.1.2 Study periods

The following study periods will be considered for analysis:

- Screening period (SCR): from the date of signing informed consent form (ICF) to, and not include the date of the first ligelizumab treatment (i.e. V201) in extension, or the first visit in the first observation period (i.e. V101), whichever comes first.
- First observation period (OBS1): from Visit 101 up to Visit 199. The duration of OBS1 period for each subject varies, as it depends on occurrence of relapse ($UAS7 \geq 16$). Maximum duration of OBS1 is 36 weeks.
- First 12 weeks of the first half of the treatment period (TRT1A): from Visit 201 to Visit 204.
- Week 12 to Week 52 of the first half of the treatment period (TRT1B): from Visit 204 to Visit 214 or 301, whichever comes first.
- Entire first half treatment period (TRT1): from Visit 201 to Visit 214 or 301, whichever comes first.
- Second observation period (OBS2): from Visit 301 up to Visit 399. The duration of OBS2 period for each subject varies, as it depends on occurrence of relapse ($UAS7 \geq 16$). Maximum duration of OBS2 is 52 weeks.
- Second half of the treatment period (TRT2): Visit 214 to Visit 9998 (excluding Visit 301 to Visit 399)
- Follow-up period:
 - Subjects who do not complete a continuous 104-week treatment will enter the follow-up period (FU12) for 12 weeks duration and will only perform Visit 9999.
 - Subjects who have completed the full 104-week treatment period without interruption will enter the follow-up period (FU52) of 52 weeks duration and will perform Visit 501 to Visit 9999 (Week 116 to Week 156).

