2.1.1.3 Study Day and Study Week

2.1.1.3.1 Study Day

Study day is defined with respect to extension and will be used for all efficacy and safety analyses. The first day of administration of study treatment (first dose) of extension study is defined as Day 1.

All other study days will be labeled relative to Day 1. For event dates on or after Day 1, study day for a particular event date will be calculated as [Date of event] - [Date of first dose] + 1. For the dates before Day 1, study day for an event date will be calculated as [Date of event] - [Date of first dose]. Hence, study days for the following critical dates are defined as follows:

- Signing ICF (Day *a*) : [Date of signing ICF] - [Date of first dose]
- Start of OBS1 (Day *b*): [Date of Visit 101] - [Date of first dose]
- Start of TRT1 (Day 1): defined as Day 1
- Start of TRT2 (Day *c*): [Date of Visit 214] - [Date of first dose] +1
- Start of OBS2 (Day *d*): [Date of Visit 301] - [Date of first dose] +1
- Start of 52-week FU (Day *e*): [Date of Visit 501] - [Date of first dose] +1

Duration of an event will be calculated as (Event end date - Event start date + 1).

The descriptor “Day 0” will not be used.

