2.5.3 Handling of missing values/censoring/discontinuations

The UAS7 score is derived from the sum of the HSS7 score and the ISS7 score, as noted above. The HSS7 and ISS7 score will be derived by adding up the daily HSS and ISS scores of the 7 days preceding the visit, respectively. The daily score (HSS and ISS) will be calculated by averaging the morning and evening HSS and ISS score, respectively. If one of the morning or evening scores is missing, the non-missing score for that day (morning or evening) will then be used as the daily score.

A minimum of 4 out of 7 daily scores are needed to reliably calculate a weekly HSS7, ISS7 or UAS7 score. For each weekly score from UPDD (i.e. HSS7, ISS7 and UAS7 score), if one or more of the daily scores are missing, the following principles will be applied to handle the missing data:

- If a subject has at least 4 “non-missing” daily scores within the 7 days prior to the study visit, the weekly score will be calculated as the sum of the available eDiary scores of that week, divided by the number of non-missing days, multiplied by 7.
- If there are less than 4 “non-missing” daily scores within the prior 7 days, then the weekly score will be considered as missing for that week.

Subjects who discontinue from study treatment early will be encouraged to stay in the study following the procedures described in the study protocol Section 9.1.1. These are considered as retrieved dropout (RDO) subjects.

The primary analysis will account for different post-dosing events for missing data handling as follows:

- Discontinuation of initially assigned study treatment prior to Week 12 (Visit 204) due to AEs or lack of efficacy or any other reasons, except for the reason of study early termination: Retrieved dropout (RDO) data collected after study treatment discontinuation will be used for analysis. If no RDO data was collected after study treatment permanent discontinuation, non-responder imputation will be applied for missing data imputation.
- Discontinuation of initially assigned study treatment prior to Week 12 (Visit 204) due to study early termination: the efficacy data collected after the discontinued treatment will be censored. The missing data caused by this intercurrent event occurrence will be imputed based on the treatment arm (ligelizumab 72 mg or 120 mg q4w) data under the missing at random (MAR) assumption using multiple imputation separately.

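### SAP Table 2-4 prints OBS2 Week 52 seven days later than its own formula gives, so the printed week starts on the scheduled exit visit

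*SAP*

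**What the plan says.** SAP Section 2.1.1.3.3, Table 2-4, sets OBS2 Week 1 as Day d to d+6 and Week x as Day 7(x-1)+d to 7x+d-1. Its last row reads "OBS2 Week 52 Day $[364 + d] \sim [d + 370". SAP Section 2.1.1.3.1 defines Day d as "Date of Visit 301] - [Date of first dose] +1", and Section 2.1.1.2 adds: "Maximum duration of OBS2 is 52 weeks".

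Protocol Table 8-2 places Visit 301 on OBS2 Day 1 and Visit 399 on OBS2 Day 365, and schedules collection of the eDiary at Visit 399 for subjects not going on to treatment. Under Protocol Section 3.4, subjects whose UAS7 is below 16 "by the end of this second observation period will perform Visit 399 (EOOBS2) of this extension study to exit the study".

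SAP Section 2.5.3 builds weekly scores by "adding up the daily HSS and ISS scores of the 7 days preceding the visit" and states: "A minimum of 4 out of 7 daily scores are needed to reliably calculate a weekly HSS7, ISS7 or UAS7 score". SAP Section 2.4.2.3.2 summarises weekly rescue tablets by study week and sets the weekly total to missing if any day is unrecorded. SAP Section 2.14.3 carries the Section 2.4 analyses into the final analysis.

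SAP Table 2-5 uses the same form of formula for the 52-week follow-up, anchored at Day e (the date of Visit 501), and prints FU Week 52 as Day e+364 to e+370.

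**The concern.** The general row and the last row of Table 2-4 give different days for the same week, and the SAP does not say which governs. The printed row places Week 52 on and after the visit at which a non-relapsing subject leaves the study and returns the diary.

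Week 52 is the end of the treatment-free period, and Protocol Section 8.3.3 says worsening after well-controlled disease is measured during OBS2. If the printed row were programmed, the last complete diary week before exit would carry no label, and the week labelled 52 would be almost empty for subjects seen on schedule.

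**Working it through.** **Step 1. Table 2-4, x = 52.**
- Start: 7 × (52 − 1) + d = d+357.
- End: 7 × 52 + d − 1 = d+363.
- The printed d+364 to d+370 is reproduced only with x = 53: 7 × 52 = 364 and 7 × 53 − 1 = 370.
- Week 51 is d+350 to d+356, so with the printed row d+357 to d+363 fall between Week 51 and Week 52.

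**Step 2. Same substitution in the end rows of the other tables.**

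| SAP table | Week | Formula gives | Printed | Agree |
|---|---|---|---|---|
| 2-1 | 52 | 358 to 364 | 358 to 364 | yes |
| 2-2a | 104 | 722 to 728 | 722 to 728 | yes |
| 2-2b | 104 | c+364 to c+370 | c+364 to c+370 | yes |
| 2-3 | OBS1 36 | b+245 to b+251 | b+245 to b+251 | yes |
| 2-4 | OBS2 52 | d+357 to d+363 | d+364 to d+370 | no |
| 2-5 | FU 52 | e+357 to e+363 | e+364 to e+370 | no |

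The offsets 364 and 370 are correct in Table 2-2b, which may be where the row was copied from.

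**Step 3. Position of Visit 399.** OBS2 Day 1 is Day d, so OBS2 Day 365 is d+364. The formula window is exactly the 7 days before that visit. The printed window is the visit day and the 6 days after it.

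**Step 4. Diary days in each window, by actual timing of Visit 399** (assuming entries stop at the visit; visit day counted / not counted):

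| Days late | Printed window | Formula window |
|---|---|---|
| 0 | 1 / 0 | 7 / 7 |
| 1 | 2 / 1 | 7 / 7 |
| 2 | 3 / 2 | 7 / 7 |
| 3 | 4 / 3 | 7 / 7 |
| 4 | 5 / 4 | 7 / 7 |
| 6 | 7 / 6 | 7 / 7 |
| 7 | 7 / 7 | 7 / 7 |

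With the printed row, a weekly symptom score needs a visit at least 3 days late (visit day counted) or 4 (not counted). The rescue total, which needs all 7 days, requires a visit at least 6 or 7 days late respectively.

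**Step 5. Table 2-5.** In Protocol Table 8-1, Visit 9998 is Day 729 (Week 104), Visit 501 is Day 813 (Week 116) and Visit 9999 (EOS) is Day 1093.
- With e = 813, EOS is 1093 − 813 = 280, that is e+280.
- The printed FU Week 52 starts 364 − 280 = 84 days after EOS; the formula value starts 357 − 280 = 77 days after EOS.
- Visit 501 comes 813 − 729 = 84 days (12 weeks) after Visit 9998. Table 2-2a ends at Day 728, so Days 729 to 812 have no study week.
- Anchored at Visit 9998 instead, formula Week 52 is 729 + 357 = 1086 to 729 + 363 = 1092, the 7 days before EOS.

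**The case against.** The other side has four points.

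1. The correct rule stands in the same table. A programmer who implements the general row gets the right days, and Section 2.5.3 separately ties weekly scores to the 7 days before the visit, which for an on-schedule Visit 399 are the same days. This stands: the loss occurs only if the printed row is followed.

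2. A reader might infer that Week 52 cannot be scored for any completer. The documents do not support that. Protocol Section 8 asks that visits take place as scheduled "or as close to the designated day/time as possible" and sets no window for Visit 399. Step 4 shows that a visit 3 or 4 days late already allows a score.

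3. No visible efficacy endpoint depends on this week. SAP Table 2-16 lists none for OBS2, and the primary and secondary diary analyses use treatment-period weeks, whose tables reproduce. This stands, with two limits: the rescue-tablet summary by study week does use these labels, and redacted analyses cannot be checked.

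4. The study was terminated early, so few subjects may have completed OBS2. That is plausible, but the documents give no number.

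A reader might also take Table 2-5 for the same slip with the same remedy. Step 5 shows otherwise: its formula value also falls after the end of the study.

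**Conclusion.** The contradiction in Table 2-4 is certain and is exactly 7 days. It does not depend on any assumption about visits.

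The consequence is conditional. It requires that the printed row be programmed and that Visit 399 be on or near schedule, with diary entries ending there. Under those conditions at most 1 of 7 days is available on the scheduled day, so the OBS2 Week 52 weekly scores and rescue total would be missing. A claim that all completers are affected goes beyond the documents.

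The visible impact is limited to a descriptive rescue-medication summary and any OBS2 diary output produced by study week. The Week 12 primary and secondary results do not change. This is a definite error in an operative window definition, with small reach and a very cheap correction.

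Table 2-5 has a separate and larger defect. Its 52-week grid starts at Visit 501 and so runs 12 weeks past EOS, whichever version of the last row is used.

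**What to change.** - **Table 2-4:** change the last row to OBS2 Week 52: Day [357 + d] ~ [d + 363].
- **Table 2-5:** either move the anchor to the start of follow-up (Visit 9998, Week 104) and print FU Week 52 as anchor+357 to anchor+363, or keep Visit 501 and end the grid at EOS. The second option gives 280 / 7 = 40 weeks, with FU Week 40 at e+273 to e+279, but leaves Days 729 to 812 unlabelled. The first is cleaner. If it is chosen, amend the definition of Day e in Section 2.1.1.3.1 to match.
- **Programming check:** confirm that the derivation of OBS2 and follow-up weeks uses the corrected rows.

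The cost is a few lines in the SAP and a check of the week derivation. No new data are needed.

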2.1.1.3.4 Study week in the 52-week follow-up period

Duration of follow-up period is 52 weeks in subjects who have completed the full 104-week treatment period without interruption and 12 weeks for all other subjects.

Study weeks (FU Week x) in the follow-up period are defined based on the study days and study day of start of FU (Day e) as indicated in Table 2-5:

Table 2-5 FU Study Week definition based on Study Day, 52-week follow-up period

FU Study Week (x)	Study Days
FU Week 1	Day $e \sim e + 6$
...	...
FU Week x	Day $[7 \times (x-1) + e] \sim [7 \times x + e - 1]$
...	...
FU Week 52	Day $[364 + e] \sim [e + 370]$

For the by visit summary tables, they will include all the information collected at the scheduled visit. The unscheduled visit information will not be included in the by visit summary table.

2.1.1.4 Baseline

2.1.1.4.1 Baseline for efficacy analyses

The baseline eDiary score corresponding to a score in the 7 days prior to the first dosing visit assessment, the baseline will be defined as the baseline week (see Table 2-1).

For DLQI/CDLQI [REDACTED], baseline is the assessment obtained at Visit 201. For a subject who receives partial dose for the first dose day of study treatment, the baseline will be still defined according to the first dosing date of the partial dose. For a subject without any administration of study dose, the baseline assessment will be his last assessment in the Extension study. If a questionnaire was completed more than once on the same date, on the last date on or before treatment start date, then the worst outcome of the duplicate observations on that date will be used as baseline.

2.1.1.4.2 Baseline for safety analyses

In general, baseline is the last assessment (including unscheduled visits) obtained on or after signing ICF and on or before the first dose of study treatment in extension. All assessments obtained after the first dose of study treatment in extension are considered as post-baseline unless otherwise specified.

For CU Index, if no evaluable outcome is available at the extension study baseline, the first evaluable post-baseline outcome will be used for summary of baseline characteristics.

For ECG numeric measurements, baseline will be defined as the mean of scheduled measurements taken at screening (Visit 1). If there is additional screening (re-screening, Visit 2) and/or unscheduled assessment(s) taken before the first dosing date, the assessment taken at

the last date on or before the first treatment dosing data will be considered as baseline for ECG measurements.

For ECG overall interpretation, baseline will be the most common interpretation (normal/abnormal) taken at the last assessment date on or before the first treatment dose date. If the subject has the same number of normal and abnormal interpretations at the same last assessment date, then the overall interpretation will be set to abnormal.

[REDACTED]

2.2 Analysis sets

Enrolled set (ENR): The ENR will include all enrolled subjects, regardless of whether or not they receive a dose of study drug.

Full Analysis Set (FAS): The FAS will include all enrolled subjects who received at least one dose of study treatment. Subjects will be analyzed according to the treatment group they have been assigned to.

Safety Set (SAF): The SAF will include all subjects who received at least one dose of study treatment. Subjects will be analyzed according to the study treatment they actually received. The safety set will be used in the analysis of all safety variables [REDACTED]. The actual treatment will be defined as the treatment received over the study. In case of error in dispensation, the actual treatment will correspond to the treatment which was given most often.

[REDACTED]

Table 2-6 Subject classification rules

Analysis set	PDevs that cause subject to be excluded	Non-PDev criteria that cause a subject to be excluded
ENR	NA	NA
FAS (Full Analysis Set)	NA	No study drug taken in the extension study
SAF (Safety Analysis Set)	NA	No study drug taken in the extension study
[REDACTED]	[REDACTED]	[REDACTED]
[REDACTED]	[REDACTED]	[REDACTED]

Note: Protocol Deviation (PDev) Codes are available from the study Data Review Plan (DRP).

For each PDev, the number and percentage of subjects for whom the deviation applies will be tabulated based on SAF by treatment group for the entire study. Other PDevs in subjects who are in the ENR set but not in the SAF set will be listed only. COVID-19 related PDev will be summarized separately based on SAF by treatment group for the entire study.

No deviation will result in exclusion from FAS or SAF in this study.

2.2.1 Subgroup of interest

2.2.1.1 Subgroup of interest supporting efficacy analysis

- CU index (positive/negative): based on baseline CU index status. If a subject has a missing baseline CU index assessment, this patient will be excluded from the subgroup analysis.
- Preceding study (C2302/C2303, C2202, and C1301): based on subject's preceding study.
- Treatment group in preceding study:
 - C2302/C2303: ligelizumab 72 mg q4w liquid in vial, ligelizumab 120 mg q4w liquid in vial, omalizumab 300 mg q4w, Placebo - ligelizumab 120 mg q4w liquid in vial
 - C2202: ligelizumab 120 mg q4w liquid in vial, ligelizumab 24 mg q4w liquid in vial, Placebo - ligelizumab 120 mg q4w liquid in vial
 - C1301: ligelizumab 120 mg q4w liquid in vial

2.2.2 Subpopulations

The following subpopulations are defined for primary and key secondary efficacy analyses:

- **Ligelizumab retreatment subpopulation** (applicable to subjects whose preceding studies are C2302 and C2303): subjects who are treated with same dosage of ligelizumab in the two core studies (C2302 and C2303) and the extension study.
- **Ligelizumab responder retreatment subpopulation** (applicable to subjects whose preceding studies are C2302 and C2303): subjects who were treated by the same dosage of ligelizumab in the two core studies (C2302 and C2303) and the extension study and achieved UAS ≤ 6 at core study week 12.

Subjects who switched from placebo to ligelizumab in core studies are not included in ligelizumab retreatment subpopulation or ligelizumab responder retreatment subpopulation.

The following subpopulations are defined for relevant secondary [REDACTED]

- **PFS subpopulation** (applicable to all SAF subjects, irrespective of preceding studies): subjects who have at least one dose of ligelizumab 120 mg q4w PFS

- **Outside-of-clinic self-administration subpopulation** (applicable to SAF subjects, irrespective of preceding studies): subjects who receive ligelizumab via self-administration outside-of-clinic at least once.
- **Monotherapy subpopulation** (applicable to SAF subjects, irrespective of preceding studies): subjects who are qualified for ligelizumab monotherapy (i.e. discontinued H1-AH background medication) per investigators' decision at week 64.
- **Continuous long term treatment subpopulation** (applicable to SAF subjects, irrespective of preceding studies): subjects with an uninterrupted treatment period of 104 weeks.
- **Long term treatment subpopulation** (irrespective of preceding studies): subjects who receive ligelizumab treatment in the second half of treatment period without entering the second observation period.
- **Long term treatment with a rest subpopulation** (irrespective of preceding studies): subjects who received one-year ligelizumab treatment and move to the second observation period before moving to the second half of the treatment period.

